8.2.3.2 Study Specific Disease History

Study specific disease history collected during the Initial Screening Period included the month and year of initial PD diagnosis and assessment of the following modified United Kingdom Parkinson Disease Society (UKPDS) brain bank criteria for Parkinsonian Syndrome:

- Diagnosis of bradykinesia (slowness of initiation of voluntary movement with progressive reduction in speed and amplitude of repetitive actions)
- Diagnosis of muscular rigidity
- Diagnosis of 4 – 6 Hz resting tremor
- Diagnosis of postural instability not caused by primary visual, vestibular, cerebellar or proprioceptive dysfunction

The duration of PD will be calculated as the time (in years) from the initial diagnosis of PD until the subject entered the Initial Screening Period. Missing months for initial PD diagnosis will be set to January resulting in the earliest possible onset and the longest possible duration.

8.2.4 Previous and Concomitant Medication

Medications are classified according to active drug substance using the World Health Organization-Drug Dictionary (WHO-DD), 01 March 2011.³ The WHO drug code has 11 digits. The generic name (required for presentation in the tables and listings) is defined by the first 6 of the 11 digits. In addition, Anatomical Therapeutic Chemical (ATC) classes are assigned to the drug code. In this study, ATC codes are defined to the third level. Although there can be multiple ATC classes for a drug, each drug will be linked with one ATC class which will be assigned manually during the coding process, based on information about the indication and route in relation to the study therapeutic area. This one ATC class will be indicated as the "primary" ATC class.

Previous or prior medications are defined as medications that were being used at the end of the previous study and were continuing to be used when the subject entered the 3005 study. Summaries of previous medications will focus on anti-parkinsonian medications.

Concomitant medications (CM) are defined as medications taken at any time during the Treatment Period defined for safety assessments in Section 6.4.6 and include medications started prior to the first 3005 LCIG infusion but continued during the study as well as medications started at or after the first 3005 LCIG infusion and before the last 3005 PEG-J exposure.

Missing and/or incomplete dates for medications are imputed in a manner resulting in the earliest onset or the longest duration. However, the Stop Date will not be imputed if the medication is reported as "Ongoing."

Technically, this will be done as follows:

- If the day is missing and the month and year are available, the start (stop) date will be completed as the first (last) day of the month.
- If the day and month are missing and the year is available, the start (stop) date will be completed as the first (last) day of the year.
- If the date is completely missing, the start (stop) date will be completed as a very early (late) date, for example, 01JAN1000 (01JAN3000).

The prevalence of concomitant anti-parkinsonian medication (CM) use during each 3005 Treatment Year will be summarized using the study day intervals described in Section 6.4.9. CM start and stop days will be calculated relative to the start of 3005 LCIG infusion (RFSTDTN) as follows:

$$\text{CM Start Day} = (\text{CM Start Date} - \text{Start of 3005 LCIG Infusion} + 1)$$

$$\text{CM Stop Day} = (\text{CM Stop Date} - \text{Start of 3005 LCIG Infusion} + 1)$$

A subject will be considered to have taken a specific CM during an interval if:

- the CM Start Day is within the study day range for the interval and was not greater than the day of the last 3005 LCIG infusion, or
- the CM Start Day is less than the lower limit of the study day range and the CM Stop Day is later than the lower limit of the study day range or missing.

Note that this definition assumes that a missing CM Stop Day is an indication that the use of the CM is ongoing. The denominator for percentage calculations for each interval will be the number of subjects whose last day of 3005 LCIG infusion was within or after the interval day range.

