6.4.6 Treatment Period

Data collected on the Date of the First 3005 LCIG Infusion (Day 1) will be assigned to the Baseline Period. However, adverse events and concomitant medications starting on Day 1 will be assigned to the Treatment Period (worst case scenario).

A Gap Period (number of days) is defined to include data collected after the end of the relevant Treatment Period in the analysis. For this study, the Gap Period will be 30 days for adverse events and 1 day for all other assessments.

For efficacy assessments the Treatment Period is defined as the Period from the Date of the First 3005 LCIG Infusion up to and including the Date of the Last 3005 LCIG Infusion + Gap Period (1 day). For safety assessments the Treatment Period is defined as the Period from the Date of the First 3005 LCIG Infusion up to and including the Date of the Last 3005 PEG-J Exposure + Gap Period (30 days for adverse events and 1 day for all other assessments).

The Endpoint value for a variable is defined as the last non-missing value assigned to the Treatment Period for the subject.

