9.6 Concomitant Medication

Concomitant medication will be presented as the number and percentage of subjects taking concomitant medication according to WHO-DD, 01 March 2011, primary ATC third level subgroup and generic name (corresponds to the first 6 digits of the 11-digit WHO-DD code). For the standard presentation, percentages will be calculated relative to the number of subjects considered valid for the Safety sample.

Subject Samples:	Tables	Safety sample and US Subset
	Listings	All subjects consented
	Figures	Not applicable
Subgroups:		Not applicable
Abbreviation:		CM

Standard Presentations

Concomitant medication assigned to the Treatment Period will be summarized as follows:

- CMT001 The number of subjects with at least one concomitant medication use in the Treatment Period will be presented by default summary statistics, where the percentage of subjects is calculated relative to the total number of subjects considered valid for the specific subject sample, that is, Safety subject sample. In addition, the number of subjects with at least one concomitant medication use within each ATC third level subgroup and generic name will be presented. The ATC third level subgroups are to be ordered alphabetically/numerically by ATC code and within ATC third level subgroup alphabetically by generic name.

All medications entered on the "Concomitant Medication" CRF form will be presented in subject data listings as follows:

- CML001 By-subject and within-subject by ascending start date/relative start day of medication use. In CML001 the relative start and stop day of concomitant medication use will be calculated relative to the start of the first infusion and will be presented for those subjects who were allocated to treatment and received at least one dose of investigational study medication. If the concomitant medication is "Ongoing" it will be indicated as such in the listing and the relative stop day will not be calculated. Only original dates will be presented in the listing even though the relative day may be based on an imputed date.
- CML002 A listing of the relevant WHO-DD coding information, sorted in the same way as CML001 will also be provided.

Study Specific Presentations

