CMT002 The number of subjects with at least one anti-parkinsonian concomitant medication used in the Treatment Period will be presented by time interval (Year 1, Year 2, Year 3, Year 4, Year 5, > Year 5) using default summary statistics, where the percentage of subjects is calculated relative to the total number of subjects considered valid for the specific subject sample, that is, Safety Sample during the given time interval. In addition, the number of subjects with at least one concomitant medication use within each ATC third level subgroup and generic name will be presented. The ATC third level subgroups are to be ordered alphabetically/numerically by ATC code and within ATC third level subgroup alphabetically by generic name.

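### SAP 8.2.4 gives concomitant medication two end dates, so an anti-parkinsonian drug started between the last LCIG infusion and PEG-J removal is counted differently in CMT001 and CMT002

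*SAP*

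**What the plan says.** **General definition (SAP 8.2.4).** "Concomitant medications (CM) are defined as medications taken at any time during the Treatment Period defined for safety assessments in Section 6.4.6". The definition includes "medications started at or after the first 3005 LCIG infusion and before the last 3005 PEG-J exposure". SAP 6.4.6 ends that period at "the Date of the Last 3005 PEG-J Exposure + Gap Period (30 days for adverse events and 1 day for all other assessments").

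**CMT001 (SAP 9.6).** This is the overall table, by ATC third-level subgroup and generic name: "The number of subjects with at least one concomitant medication use in the Treatment Period will be presented by default summary statistics".

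**By-year rule (SAP 8.2.4).** A subject counts in a treatment year under either of two clauses:
- The drug starts inside the year's day range and its start day "was not greater than the day of the last 3005 LCIG infusion".
- The drug started before the year's lower limit and "the CM Stop Day is later than the lower limit of the study day range or missing". This clause has no cap at the last infusion or at the last PEG-J exposure.

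The denominator is "the number of subjects whose last day of 3005 LCIG infusion was within or after the interval day range".

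**CMT002 (SAP 9.6).** The table that uses the by-year rule is described with the longer window: "The number of subjects with at least one anti-parkinsonian concomitant medication used in the Treatment Period will be presented by time interval".

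SAP 10.1, which lists changes to the planned analyses, does not mention the two end dates.

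**The concern.** The SAP keeps two end dates: last infusion (RFENDTN) and last PEG-J exposure (RFENDT2N). SAP 6.4.1 sets the second to the PEG-J removal date when removal follows the last study drug. Protocol 11.3 records medication through post-study follow-up, so drugs started between the two dates are in the database.

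Protocol 6.2 lists concomitant medication usage among the safety and tolerability assessments, Protocol 13.3 promises a summary over time, and Protocol 7.1 recommends withholding other PD treatments where appropriate. A drug added to LCIG and a drug that replaces it after stopping answer different questions. Under the present text, the same replacement drug can be present in one table, absent from the other in the year it began, and then present again in years when the subject is no longer in the denominator. A by-year percentage whose numerator is not a subset of its denominator cannot be read as a prevalence.

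**Working it through.** The plan states no figure on this point, so there is none to reproduce. The check is to write out the rules and run example subjects through them.

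**Notation (study days).** L = last LCIG infusion; P = last PEG-J exposure; S = drug start; E = drug stop (missing means ongoing); a and b = lower and upper limits of a treatment year. From SAP Table 3, Year 2 is 366 to 730, Year 3 is 731 to 1095, Year 4 is 1096 to 1460, Year 5 is 1461 to 1825, and the last category is above 1825.

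**Rules for a drug started after Day 1.**
- CMT001: S < P by the wording of 8.2.4, or S ≤ P + 1 by 6.4.6.
- CMT002 numerator, clause 1: a ≤ S ≤ b and S ≤ L.
- CMT002 numerator, clause 2: S < a, and E > a or E missing.
- CMT002 denominator: L ≥ a.

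**Example subjects.** All day numbers are assumed.

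| Case | L | P | S | E | CMT001 | CMT002 numerators | CMT002 denominators |
|---|---|---|---|---|---|---|---|
| A | 600 | 621 | 603 | ongoing | yes | Years 3, 4, 5, >5 | Years 1, 2 |
| B | 600 | 621 | 603 | 650 | yes | none | Years 1, 2 |
| C | 725 | 746 | 728 | 760 | yes | Year 3 | Years 1, 2 |
| D | 600 | 621 | 500 | ongoing | yes | Years 2, 3, 4, 5, >5 | Years 1, 2 |

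- **A.** 603 < 621, so CMT001 counts the drug. In Year 2, clause 1 rejects it because 603 > 600. In Year 3, 603 < 731 and E is missing, so clause 2 counts it, and likewise in every later year. The subject is not in the Year 3 denominator because 600 < 731.
- **B.** As A, but 650 < 731, so clause 2 fails. The drug is in CMT001 and in no CMT002 year.
- **C.** 728 > 725 excludes it from Year 2. In Year 3, 728 < 731 and 760 > 731 include it, although 725 < 731 keeps the subject out of that denominator.
- **D.** This is a genuine add-on, started while LCIG was running. Year 2 is correct, since 500 ≤ 600. The later years are again numerator entries without a denominator, so a start-date cap alone does not cure clause 2.

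If the PEG-J comes out on the day of the last infusion (L = P = 600), a drug started on day 603 is outside the definition of concomitant medication altogether, and no conflict arises.

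**Width of the conflict.** For a gap of g = P − L days (g ≥ 1), the start days that the general definition admits and clause 1 rejects number g − 1 under 8.2.4 and g + 1 under 6.4.6. The documents do not give g. For assumed gaps:

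| g (days) | 8.2.4 wording | 6.4.6 wording |
|---|---|---|
| 7 | 6 | 8 |
| 14 | 13 | 15 |
| 28 | 27 | 29 |
| 56 | 55 | 57 |

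The two columns differ because 8.2.4 stops before the last PEG-J exposure while 6.4.6 runs one day past it.

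**With S ≤ L and L ≥ a added to both clauses.** Cases A, B and C fall out of CMT002 entirely, since 603 > 600 and 728 > 725. Case D is counted in Year 2 only. Every numerator then lies within its denominator.

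**The case against.** The best defence is that the longer CMT001 window is deliberate. SAP 6.4.1 treats LCIG as a therapeutic system that includes the device, SAP 6.4.6 runs all safety assessments to the end of PEG-J exposure, and medication use is a safety assessment. CMT001 covers all drugs and specifies no overall count of anti-parkinsonian users. CMT002 is the table meant for those drugs, and its start rule and denominator already use the last infusion. The listings CML001 (drug start and stop days) and EXL001 (last infusion date) let a reader identify later starts. This stands as a reason to keep the PEG-J window in CMT001. It does not explain why 9.6 gives CMT002 the same Treatment Period, nor does it justify the uncapped carry-over clause.

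The defence is also right that the gap should be short. Protocol Table 2 places PEG-J removal at the termination visit. Ongoing subjects at the 2015 interim have both end dates set to the Cutoff Date, so they have no gap. Subjects moving to commercial product keep the tube. Night-time oral levodopa-carbidopa is permitted (Protocol 10.6.2), and a subject already counted for that generic name adds nothing new.

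A reader might infer that such a drug never appears in CMT002. Case B fits that, but cases A and C do not. A reader might also infer that CMT001 presents these drugs as add-on to LCIG and so overstates the need for them. The SAP says only that they were used in the Treatment Period, which is true of them. Nor do the documents show that the levodopa monotherapy subgroup is misclassified: SAP 8.1.2 gives no medication window for it.

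**Conclusion.** The inconsistency is real and minor. An anti-parkinsonian drug started after the last infusion and before PEG-J removal is counted in CMT001 and omitted from CMT002 in its starting year. If it is still in use past the next year's lower limit, it is counted in later-year CMT002 numerators for a subject outside those denominators. The second fault also affects drugs started before the last infusion and still ongoing (case D). Both conclusions take the two clauses as written; a programmer might restrict numerators to denominator subjects, but the SAP does not say so.

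The number of subjects cannot be computed, because the documents give neither the gap nor the number starting a drug within it. The table conflict concerns subjects who have ended the study with a PEG-J end date later than their last infusion, chiefly those who stop LCIG and have the tube removed later. Given the planned timing of removal, the number is probably small. Multiplying guessed shares, such as 10% to 30% stopping and 25% to 75% of those starting a drug in the gap, would give 0.10 × 0.25 = 2.5% to 0.30 × 0.75 = 22.5%. The documents support neither input, so that range should not be quoted as a size.

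**What to change.** 1. In the by-year rule of SAP 8.2.4, require a start on or before RFENDTN in both clauses for anti-parkinsonian drugs.
2. In the same rule, count a subject in a year's numerator only if the subject is in that year's denominator.
3. In SAP 9.6, replace the reference to the Treatment Period in the CMT002 description with this rule.
4. In CMT001, keep the PEG-J window for all drugs, but flag or show separately anti-parkinsonian drugs started after RFENDTN, or state why the two tables use different windows.
5. While editing, make the end of the window in 8.2.4 agree with the extra day in 6.4.6.

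The cost is a few sentences, some date conditions in the programs, and one extra row or listing flag. The by-year program serves both the Safety sample and the Efficacy sample US subset (SAP 12.2), so one change covers both outputs. All dates needed are already defined, and no new data are required.

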8.3 Study Drug Accountability and Treatment Exposure

8.3.1 Study Drug Accountability

LCIG is dispensed in 100 mL medication cassette reservoirs that are designed to be connected to a portable subject-operated pump. Subjects are to return all used as well as all unused cassettes to the site at each clinic visit.

8.3.2 Duration of Study Drug and PEG-J Exposure

The duration of LCIG exposure as well as the duration of PEG-J exposure will be summarized for 3005 as well as overall. The duration of 3005 LCIG infusion (LDA) is described in detail in Section 6.4.1 (General Definitions). The duration of 3005 PEG-J exposure will be calculated as the Date of the Last 3005 PEG-J Exposure (as defined in Section 6.4.1) – the Date of the First 3005 LCIG Infusion (as defined in Section 6.4.1) +1. The total subject-years of exposure will be calculated as the sum of all subject exposures in days divided by 365.25.

As previously described, Study 3005 is an extension of the previous Studies 3001, 3002, 3003, and 3004. To determine the overall duration of each subject's LCIG and PEG-J exposure, the date of initial PEG-J placement and the date of initial LCIG infusion will be retrieved from the relevant study database. The overall duration of LCIG infusion will be

calculated as the Date of the Last 3005 LCIG Infusion – the Date of the Initial LCIG Infusion +1. The overall duration of PEG-J exposure will be calculated as the Date of Last 3005 PEG-J Exposure – the Date of the Initial PEG-J placement +1.

8.3.3 Prescribed Dose

The prescribed dose of LCIG is comprised of a morning dose, a continuous maintenance dose, and an extra dose to be administered as needed. Each subject's pump settings for the morning dose, extra dose and continuous infusion rate are individually optimized and programmed by the Investigator at a clinic visit. Subjects self-administer LCIG by starting and stopping the pump each day and by infusing extra doses as needed during the continuous infusion.

8.3.4 Dose Administered

Beginning with Protocol Amendment 4, subjects enrolled at US sites were to record all LCIG infusions (including pump start time, pump stop time and the time of any extra dose administration) and all oral levodopa/carbidopa doses on a Daily Dosing Diary for the 3 days before each clinic visit. The average total daily LCIG dose at the final 3005 visit will be calculated by summing the total mL of LCIG infused on each Daily Dosing Diary completed within 14 days of the final Daily Dosing Diary and dividing by the number of diaries recorded. The average total daily dose of LCIG will then be converted to the average total daily dose of levodopa using the conversion factor of 1 mL LCIG = 20 mg levodopa. Only diaries reporting at least 12.8 hours of pump operation will be included in this calculation.

The average total daily levodopa dose at the final 3005 visit will be summarized with descriptive statistics for each component (morning dose, continuous maintenance dose, and extra dose) as well as for the total levodopa dose. Each subject's total daily levodopa dose at the end of their initial LCIG titration in Studies 3001, 3002, 3003 or 3004 will be retrieved from the relevant database. The total daily levodopa dose at the end of initial LCIG titration and the change in total daily levodopa dose from the end of initial LCIG titration to final 3005 visit will be summarized with descriptive statistics. To evaluate the

robustness of observations, the same summary will be prepared after grouping subjects based on the study in which they received their first LCIG infusion.

8.4 Efficacy Analysis Variables

The original Protocol included the following efficacy measures:

- Parkinson's Disease Diary⁴
- Parkinson's Disease Questionnaire (PDQ-39)
- Clinical Global Impression – Improvement (CGI-I)

These measures were removed from the schedule of assessments with Protocol Amendment 1. With Protocol Amendment 4, the following measures were added to the schedule of assessments for subjects enrolled at US sites:

- Parkinson's Disease Diary
- Unified Parkinson's Disease Rating Scale (UPDRS)
- Parkinson's Disease Questionnaire (PDQ-39)

The change in each efficacy measure from 3005 baseline to 3005 final visit will be determined and summarized. To provide context, the change in each efficacy measure from initial LCIG infusion to 3005 final visit will also be determined and summarized.

8.4.1 Parkinson's Disease Diary (PD Diary)

The core of the Parkinson's Disease Diary (PD Diary)⁴ is the questionnaire that the subject will use to record parkinsonian symptoms. The subject and/or caregiver will be prompted to answer the PD questionnaire on whether the subject has been "on" without dyskinesia, "on" with non-troublesome dyskinesia, "on" with troublesome dyskinesia, "off," or "asleep." The diary is completed for the full 24 hours of each day reflecting both time awake and time asleep. On the recording days, subjects will be instructed to make an entry every 30 minutes during their normal waking time and upon awakening from time

asleep. Beginning with Protocol Amendment 4, US subjects were to complete a PD Diary during the 3 consecutive days prior to each clinic visit.

Average normalized "off" time will be calculated as follows:

Valid Diary Days

1. For subjects with more than one observation for the same 30 minute time period, the 30-minute time will be evenly split among the number of observations checked.
2. Subjects who do not complete at least 12 awake hours of symptom diary data (not including "ASLEEP" time) will have that daily data set to missing (i.e., will not be considered as a valid symptom diary day). There will be no imputation of data for these diary days.

Absolute and Normalized Daily "OFF" Time

3. Absolute "off" time, "on" time without dyskinesia, "on" time with non-troublesome dyskinesia, "on" time with troublesome dyskinesia and "asleep" time will be determined from each 24-hour PD symptom diary.
4. Daily awake time is the sum of absolute "off" time, "on" time without dyskinesia, "on" time with non-troublesome dyskinesia, and "on" time with troublesome dyskinesia.
5. "Off" time, "on" time without dyskinesia, "on" time with non-troublesome dyskinesia, and "on" time with troublesome dyskinesia will be normalized to a 16 hour waking time due to the variance in sleep patterns. For example, normalized "off" time is calculated as:

$$\text{Normalized "off" time} = (\text{Absolute "off" time} / \text{Awake time}) * 16.$$

All times are expressed in decimal hours.

Daily Average

6. Valid symptom diary days (at least 12 awake hours) will be used to compute the average daily normalized "off" time. For post-baseline visits, the valid symptom diary day must be within 7 days of the clinic visit but not on or after the day of the clinic visit. If more than 3 valid symptom diary days are available, the 3 days closest to the clinic visit will be used.
7. If only 2 valid symptom diary days are available prior to a clinic visit, data from the 2 days will be used to calculate the average daily normalized "off" time.
8. If only one valid symptom diary day is available the average daily from the previous visit will be averaged with the daily normalized "off" time from the one valid diary day.
9. Subjects that do not have any valid symptom diary days for a visit or who are completely missing a visit will have the average daily normalized "off" time set to missing for that visit.

The change from baseline in average daily normalized "on" time with troublesome dyskinesia, normalized "on" time with non-troublesome dyskinesia, and normalized "on" time without dyskinesia will be calculated for each subject using the 3 diary days prior to the visit and the same strategy employed for the calculation of normalized "off" time. Normalized "on" time without troublesome dyskinesia will be calculated for each PD Diary as the sum of normalized "on" time without dyskinesia and normalized "on" time with non-troublesome dyskinesia.

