6.3 Visit Names and Labels

The visit names/labels to be used in the analysis data sets and in the TLFs are defined in [Table 1](#) below.

Table 1. Visit Names and Labels

Visit Number	Visit Name	Visit Label
1	Baseline	Baseline
2	Month 6	Month 6
3	Month 12	Month 12
4	Month 18	Month 18
5	Month 24	Month 24
6	Month 30	Month 30
7	Month 36	Month 36
8	Month 42	Month 42
9	Month 48	Month 48
10	Month 54	Month 54
11	Month 60	Month 60
12	Month 66	Month 66
13	Month 72	Month 72
14	Month 78	Month 78
15	Month 84	Month 84
99	Follow-up	Follow-up

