6.4.5 Baseline Period for Study 3005

The Baseline Period for Study 3005 is defined as the time before the first 3005 LCIG infusion. For efficacy measures, the final value in the previous study (Study 3003 or Study 3004) will be retrieved from the relevant database and will be considered the 3005 baseline value. For safety evaluations, the final assessment in the previous open-label LCIG study or in 3005 that is on or before the date of the first 3005 LCIG infusion will be used as the 3005 Baseline value. For systolic blood pressure, diastolic blood pressure and

pulse, the final assessment where results are present for both the supine and standing position will be considered baseline.

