9.9 Efficacy Analyses

Subject Samples:	Tables	Efficacy Sample and US Subset
	Listings	All subject consented
	Figures	Not applicable
Subgroups:		First LCIG infusion study (3001/3002, 3003 or 3004), troublesome dyskinesia at initial LCIG infusion (< 1 hour, > 1 hour), dose of levodopa at initial LCIG infusion (< 1250 mg/day, > 1250 mg/day), and levodopa monotherapy during Study 3005 (yes, no)
Abbreviation:		QS

Standard Presentations

QST001 The average daily normalized "off" time will be summarized at initial LCIG infusion, at 3005 baseline and at 3005 endpoint as well as the change from initial LCIG infusion to 3005 endpoint and the change from 3005 baseline to 3005 endpoint. Descriptive statistics (including n, mean, minimum, maximum and 95% confidence interval) will be calculated.

Statistical tests for within group changes from initial LCIG infusion and from 3005 baseline will be implemented using PROC UNIVARIATE.

For the UNIVARIATE the following SAS[®] code will be used:

*PROC UNIVARIATE data = <SAS[®]-dataset> cibasic alpha = 0.05;
VAR OFFTIME;*

RUN;

The same methods defined above for average daily normalized "off" time will also be used to analyze the following assessments:

1. Change in average daily normalized "on" time without troublesome dyskinesia
2. Change in average daily normalized "on" time with troublesome dyskinesia
3. Change in average daily normalized "on" time with non-troublesome dyskinesia
4. Change in average daily normalized "on" time without dyskinesia
5. Change in the UPDRS total score, subscores of Parts I – IV and Part IV Questions 32, 33 and 34 (Dyskinesia items)
6. Change in the PDQ-39 summary index and each domain score

Variables derived from the PD Diary and PDQ-39 will be summarized for the Efficacy sample and the US subset of the Efficacy sample.

Variables derived from the UPDRS will be summarized for the US subset of the Efficacy sample.

QST002 The change from initial LCIG infusion to 3005 endpoint and from 3005 baseline to 3005 endpoint will be summarized by subgroup in the Efficacy sample – US Subset for the PD Diary variables.

QST003 The CGI score at 3005 endpoint will be summarized using the appropriate default summary statistics for the Efficacy sample.

Subject data listings will include:

- QSL001 A listing of Parkinson's Disease Diary data by-subject and within-subject by visit will be presented.
- QSL002 A listing of CGI-I scores by-subject and within-subject by visit will be presented.

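### A visit with one valid diary day is averaged 50:50 with the previous visit, so a subject's change from 3005 baseline is exactly halved whenever the borrowed value is that baseline

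*SAP*

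**What the plan says.** SAP section 8.4.1 sets the diary value for a visit by the number of valid days.

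- Two days (item 7): "If only 2 valid symptom diary days are available prior to a clinic visit, data from the 2 days will be used" for the average, and nothing else enters.
- One day: item 8 states "If only one valid symptom diary day is available the average daily from the previous visit will be averaged with the daily normalized", where the last words refer to that single day's off time. No weights are given, so the plain reading is one half each.
- No days (item 9): "Subjects that do not have any valid symptom diary days for a visit or who are completely missing a visit" get a missing value.

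The same section applies this strategy to the on-time variables. It does not define the previous visit. Table 1 in SAP section 6.3 lists Baseline as Visit 1 and Month 6 as Visit 2.

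For efficacy, SAP section 6.4.5 takes baseline from the preceding open-label study: "the final value in the previous study (Study 3003 or Study 3004) will be retrieved from the relevant database". Section 10.1 explains that this replaces the protocol's first-study baseline, so that the analysis addresses maintenance during 3005. The endpoint is defined in section 6.4.6: "The Endpoint value for a variable is defined as the last non-missing value assigned to the Treatment Period for the subject". Section 9.9 then gives a 95% confidence interval and a test: "Statistical tests for within group changes from initial LCIG infusion and from 3005 baseline will be implemented using PROC UNIVARIATE".

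On the original protocol's efficacy measures, the PD Diary among them, SAP section 8.4 says: "These measures were removed from the schedule of assessments with Protocol Amendment 1". The diary returned at US sites with Amendment 4.

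**The concern.** Item 8 is the only diary rule that brings in data from another visit. Because the SAP moved the efficacy baseline to the end of the preceding study, the borrowed value can be the comparator itself. The change is then a contrast between baseline and something that is half baseline.

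This can arise in two ways:

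- **A one-day Month 6 visit.** Baseline is the visit before it in Table 1.
- **A one-day first diary after the Amendment 1 to 4 gap**, if the previous visit means the last visit with a diary value.

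If the term instead means the immediately preceding visit, and that visit had no diary, item 8 has no input and cannot be applied. A programmer would have to guess.

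The question put to these data is whether efficacy was maintained. A rule that pulls affected subjects toward no change favours a positive answer if they are in fact worsening.

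**Working it through.** The plan states no figure to reproduce here. The inputs are the rules above. The documents give neither the frequency of one-day endpoints nor any SD, so those are assumptions.

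**One subject.** Let B be the 3005 baseline, P the previous visit's value and D the single valid day. Item 8 gives V = (P + D)/2.

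- P = B: V − B = (B + D)/2 − B = (D − B)/2. With B = 3 h and D = 5 h, the change is +1.0 h instead of +2.0 h. With D = 1 h it is −1.0 h instead of −2.0 h.
- P ≠ B: V − B = [(P − B) + (D − B)]/2. With B = 3, P = 4 and D = 5, the change is 1.5 h against 2.0 h, a milder shrinkage.
- Change from initial LCIG infusion: shifted but not halved. With an initial value of 6.5 h, B = 3 and D = 5, item 8 gives 4 − 6.5 = −2.5 h, against 5 − 6.5 = −1.5 h with the day alone.

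**Group mean.** Let f be the share of endpoints resting on one valid day and g the share of those that borrow baseline. Assume the same mean change in all subjects and linear drift. A one-day endpoint at month T that borrows from a diary six months earlier loses L = 0.5 × 6/T of its change: 0.25 at T = 12 and 0.0625 at T = 48. It therefore retains 75% or about 94%. The group retains 1 − f × [0.5g + (1 − g)L].

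| Assumption | f = 10% | f = 20% | f = 30% |
|---|---|---|---|
| g = 1 | 95% | 90% | 85% |
| g = 0.5, L = 0 | 97.5% | 95% | 92.5% |
| g = 0.5, T = 48 | 97.2% | 94.4% | 91.6% |
| g = 0.5, T = 12 | 96.3% | 92.5% | 88.8% |

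**Interval and test.** These come from a simulation with 8,000 replicates and assumed inputs: true change 1.0 h, between-subject baseline SD 2.5 h, change SD 2 h, day-to-day SD 2 h, baseline and full visits as three-day means. For n = 100 and g = 1:

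| | f = 10% | f = 20% | f = 30% |
|---|---|---|---|
| Item 8: mean estimate (h) | 0.951 | 0.899 | 0.851 |
| Item 8: coverage of true value | 94.6% | 93.6% | 89.9% |
| Item 8: coverage around its own mean | 94.9% | 95.5% | 94.8% |
| Item 8: mean SE (h) | 0.249 | 0.241 | 0.232 |
| Single day: mean estimate (h) | 1.000 | 0.996 | 1.000 |
| Single day: coverage of true value | 94.6% | 94.5% | 95.2% |
| Single day: mean SE (h) | 0.263 | 0.268 | 0.273 |

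The interval under item 8 is correctly sized around its own mean. The loss of coverage comes from the shifted mean, not from an understated standard error. At n = 50 and f = 20%, the share of tests with p < 0.05 is 0.735 under item 8, 0.730 with the single day and 0.668 if two days are required.

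**The case against.** **Reach.** Halving matters only if the endpoint itself is affected. A Month 6 endpoint resting on one day is a narrow case: subjects in the earlier interim (cutoff 04 May 2012) were more than 19 months further on by the protocol date of 17 December 2013. The second route depends on one reading of an undefined term. This stands as a limit on g, and the undefined term is a defect under either reading.

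**Frequency.** Three diary days per visit, reminder calls, refresher training and a seven-day window should all make one-day visits uncommon. At an assumed f = 5% and g = 0.5, retention is 1 − 0.5 × 0.05 × 0.5 = 98.75%. This stands too: the algebra is certain and the group effect is not.

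**Total error.** Item 8 trades bias for variance. With the simulated inputs above (n = 100, g = 1), root mean squared error under item 8 against the single day is 0.256 v 0.266 h at f = 10%, 0.261 v 0.269 at 20% and 0.276 v 0.272 at 30%. With g = 0.5 item 8 is lower at every f tested. The advantage is small and depends on the inputs: at a true change of 2.0 h and f = 20% it reverses to 0.319 v 0.272. It is also gained by shrinking toward the comparator, which a maintenance analysis should avoid.

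**Consequence.** The primary objective is access, the primary statistical objective is safety, the protocol lists alpha as not applicable, and there is no maintenance margin. If subjects improve, the shrinkage is conservative. UPDRS and PDQ-39 are untouched. These points argue against a higher severity, not against a correction.

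**Timing and comparability.** The SAP covers an interim with a lock completed in October 2015, and the diary rule behind the 3003 and 3004 baselines is not visible. Changing only the 3005 rule could create a mismatch. This is a real cost, and running the present rule alongside would show its size.

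**Conclusion.** The concern holds. Where the borrowed value is the 3005 baseline, the halving is an identity and needs no assumption beyond equal weights, which is what averaging two quantities means. A blended value can be the endpoint and so enter the tested change from 3005 baseline for all PD Diary variables.

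The size at group level cannot be fixed from the documents. Over the assumed f of 10% to 30%, the mean retains 85% to 95% of the change if every one-day endpoint borrows baseline. With g = 0.5 it retains 88.8% to 97.5%, depending on the loss in the others. Below f = 10% the effect is smaller still. The direction is always toward the borrowed value.

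This should be corrected. It is not critical, because efficacy is a secondary objective and the effect may be small. But the plan currently gives the reader no means of telling how much of any reported stability is borrowed baseline.

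**What to change.** Replace item 8 in SAP section 8.4.1 with text such as:

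> When a visit has a single valid symptom diary day, the normalized value for that day is the visit value. No value from any other visit, baseline included, is combined with it. The rule holds for every PD Diary variable.

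In addition:

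- Report the number and percentage of 3005 endpoints that rest on one, two and three valid days.
- Add a sensitivity analysis requiring at least two valid days, with the endpoint falling back to the last visit that meets the requirement.
- Run the present item 8 alongside, with the previous visit defined as the last visit with a diary value, to check comparability with the earlier studies.

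The cost is one SAP sentence, one count table and a small programming change. The SAP should name which diary tables are repeated, since section 12.2 lists 10 main and 20 subgroup diary tables. One-day values become somewhat noisier: mean SE about 0.27 h against 0.24 h at f = 20% and n = 100 under the assumed inputs. A difference from the rule behind the 3003 and 3004 values is possible, and the parallel run would show it.
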